9.2. Distributional assumptions and outlying responses

Distributional assumptions (e.g. normality of regression residuals for continuous outcomes) will be assessed visually prior to analysis; although in the first instance the proposed primary method of estimation in this analysis plan will be followed. If responses are considered to be particularly skewed and/or distributional assumptions violated, other analytical options will be considered such at the transformation of responses prior to analysis (e.g. log transformation) or the use of medians and interquartile ranges alongside unadjusted differences in medians using bootstrapping methods (repetition=1000, seed=271123).

If extreme values are apparent and considered to be affecting the integrity of the analysis, a sensitivity analysis consisting of removing the outlying response(s) and repeating the analysis will be performed. Output from these analyses, if performed, will be described and presented alongside the original analysis (or included, e.g. in appendices) with the excluded values clearly labelled. See section 9.10 for further details regarding sensitivity analyses.

9.3. Handling missing data

In the first instance, analyses will be completed on received data only with every effort made to follow-up participants to minimise any potential for bias. To examine the possible impact of missing data on the results, and to make sure we are complying with the intention-to-treat principle, sensitivity analysis will be performed on the primary outcome measure.⁶ See section 9.10 for further details regarding sensitivity analyses.

9.4. Data manipulations

The trial statistician will derive all responses from the raw data recorded in the database:

Other:

• Maternal age at randomisation (years)

(Date of randomisation-date of birth)/365.25.

Outcome Measures:

Primary Outcome

• Live births at and beyond 34 completed weeks of gestation, as a proportion of all women randomised.

CRF: LOCI: 07. Pregnancy Outcome Form **Question:**

AND \circ `Gestation at pregnancy end' = \geq 34 weeks
Exclude participants where: pregnancy outcome is miscarriage, ectopic, still birth or termination and any participants who had a live birth <34 weeks. Participants will be censored if they withdraw or are lost to follow-up before pregnancy end. They will be censored at the point of withdrawal/lost to follow-up. Secondary outcomes
Treatment outcomes:
Number of ovulation induction cycles to live birth
 CRF: LOCI: 04. End of Ovulation Induction/Pregnancy Confirmation Form Question: `Number of completed OI treatment cycles?' `Did the participant become pregnant within 240 days (8 months) of randomisation?' = Yes
CRF: LOCI: 07. Pregnancy Outcome Form Question: • Was the baby born alive? = Yes
No. of women who ovulated
 CRF: LOCI: 03. OI Drug Compliance and Ovulation Tracking Form Question: 'Was an LH surge confirmed?'= Yes OR 'Progesterone concentration' = >20 nmol/l OR USS follicular tracking 'Was ovulation demonstrated?' = Yes
If any of these criteria are fulfilled at any one of the treatment cycles, then this would indicate

• 'Was the baby born alive?' = Yes;

If any of these criteria are fulfilled at any one of the treatment cycles, then this would indicate that ovulation has occurred.

Ovulation rate (total number of ovulations / total number of ovulation induction cycles)

TOTAL NUMBER OF OVULATIONS:

CRF: LOCI: 03. OI Drug Compliance and Ovulation Tracking Form

Question:

• 'Was an LH surge confirmed?'= Yes

OR

• 'Progesterone concentration' = >20 nmol/l

OR

USS follicular tracking

• 'Was ovulation demonstrated?' = Yes

Obtain total number of ovulations by totalling each 03. OI Drug Compliance and Ovulation Tracking Form per cycle where ovulation has occurred.

TOTAL NUMBER OF OVULATION INDUCTION CYCLES

CRF: LOCI: 04. End of Ovulation Induction/Pregnancy Confirmation form **Question:**

• 'Number of completed OI treatment cycles?'

OVULATION RATE = Total number of ovulations / Total number of ovulation induction cycles

• Time from randomisation to pregnancy

CRF: LOCI: 04. End of Ovulation Induction/Pregnancy Confirmation Form

Question:

Did the participant become pregnant within 240 days (8 months) of randomisation?' = Yes;

AND

 \circ 'If yes, date of positive pregnancy test:' = Use date

Time to pregnancy (weeks) = ((Date of positive pregnancy test)-(Randomisation Date))/7

• Number of ovulation induction cycles required for pregnancy

CRF: LOCI: 04. End of Ovulation Induction/Pregnancy Confirmation Form **Question:**

- \circ `Number of completed OI treatment cycles?'
- $\circ~$ 'Did the participant become pregnant within 240 days (8 months) of randomisation?' = Yes

Pregnancy end outcomes:

• Ongoing pregnancy at 12 weeks (range 11 to 14 weeks) of gestation

CRF: LOCI: 05. Pregnancy Booking Scan Form

Question:

 \circ `Did the woman undergo a booking scan at 11-14 weeks?' = Yes

AND

- \circ 'Gestation according to ultrasound scan:' = range 11 to 14 weeks
- 'Fetal heart beat present' = For each fetus

• Pregnancy loss (defined as pregnancy loss before 24 weeks of gestation)

CRF: LOCI: 07. Pregnancy Outcome Form

Question:

• 'Was the baby born alive?' = No;

AND

```
\circ 'Gestation at pregnancy end' = <24 weeks;
```

AND

 `If no, what was the pregnancy outcome:' = Miscarriage, Ectopic pregnancy, Molar pregnancy, Pregnancy of unknown location, Termination

• Twin live births

CRF: LOCI: 05. Pregnancy Booking Scan Form

Question:

 \circ 'Did the woman undergo a booking scan at 11-14 weeks?' = Yes

AND

• 'Fetal heart beat present' = For each fetus

AND

 \circ 'If more than 1 fetus, type of multiple pregnancy:' = List type

CRF: LOCI: 07. Pregnancy Outcome Form

Question:

CHECK FOR EACH FORM FOR EACH BABY

- \circ 'Was the baby born alive?' = Yes
- Gestational age at live birth

CRF: LOCI: 07. Pregnancy Outcome Form **Question:**

• 'Was the baby born alive?' = Yes

AND

• 'Gestation at pregnancy end:' = Use gestation

Where live birth ≥ 24 weeks:

```
Time from conception to delivery (gestational age)
•
CRF: LOCI: 07. Pregnancy Outcome Form
Question:
   \circ 'Was the baby born alive?' = Yes
AND
      'Gestation at pregnancy end:' = \geq24 weeks
   0
AND
     'Gestation at pregnancy end:' = Use Gestation
   0
   Gestational age <28/<32/<37 weeks
٠
CRF: LOCI: 07. Pregnancy Outcome Form
Question:
   \circ 'Was the baby born alive?' = Yes
AND
      'Gestation at pregnancy end:' = \geq24 weeks
   0
Categorise Gestational age at pregnancy end by: <28/<32/<37 weeks.
   Singleton live births at and beyond 34 completed weeks of gestation
CRF: LOCI: 05. Pregnancy Booking Scan Form
Question:
   • 'Number of fetus(es)?' = 1
CRF: LOCI: 07. Pregnancy Outcome Form
Question:
     'Was the baby born alive?' = Yes
   0
AND
   ◦ 'Gestation at pregnancy end:' = \geq34 weeks
  Live births at and beyond 37 completed weeks of gestation
•
CRF: LOCI: 07. Pregnancy Outcome Form
Question:
   \circ 'Was the baby born alive?' = Yes
AND
     'Gestation at pregnancy end:' = \geq 37 weeks
   0
```

```
Mode of birth (unassisted vaginal, instrumental vaginal, elective caesarean
٠
   section, emergency caesarean section, vaginal breech birth, other)
CRF: LOCI: 07. Pregnancy Outcome Form
Question:
   \circ 'Was the baby born alive?' = Yes
AND
      'Gestation at pregnancy end:' = \geq24 weeks
   0
AND
     'Mode of birth' = unassisted vaginal, instrumental vaginal, elective caesarean section,
   0
      emergency caesarean section, vaginal breech birth, other
   Birth weight
•
CRF: LOCI: 07. Pregnancy Outcome Form
Question:
   \circ 'Was the baby born alive?' = Yes
AND
   ◦ 'Gestation at pregnancy end:' = \geq24 weeks
AND
     'Birth weight'
   0
   APGAR score <7 out of 10 (at 1, 5 and 10 minutes)
CRF: LOCI: 07. Pregnancy Outcome Form
Question:
   0
     'Was the baby born alive?' = Yes
AND
      'Gestation at pregnancy end:' = \geq24 weeks
   0
AND
   • 'Appar at 1 minute:' = <7
   • 'Apgar at 5 minutes:' = <7
   • 'Apgar at 10 minutes:' = <7
```

Antenatal outcomes:

Antepartum haemorrhage **CRF:** LOCI: 07. Pregnancy Outcome Form **Question:** \circ 'Was the baby born alive?' = Yes AND 'Antepartum haemorrhage?' = Yes 0 **CRF:** LOCI: 08. Maternal Outcome Form **Question:** • 'Did the woman suffer antepartum haemorrhage?' = Yes Pregnancy-induced hypertension • **CRF:** LOCI: 07. Pregnancy Outcome Form **Question:** \circ 'Was the baby born alive?' = Yes AND • 'Hypertension / pre-eclampsia?' = Yes CRF: LOCI: 08. Maternal Outcome Form **Question:** \circ 'Did the woman suffer pregnancy induced hypertension?' = Yes Pre-eclampsia CRF: LOCI: 07. Pregnancy Outcome Form **Question:** \circ 'Was the baby born alive?' = Yes AND 'Hypertension / pre-eclampsia?' = Yes 0 CRF: LOCI: 08. Maternal Outcome Form **Question:** \circ 'Did the woman suffer pre-eclampsia?' = Yes **Obstetric cholestasis** •

CRF: LOCI: 08. Maternal Outcome Form **Question**:

 \circ 'Did the woman suffer obstetric cholestasis?' = Yes

```
Preterm (<37 weeks) pre-labour rupture of membranes
٠
CRF: LOCI: 07. Pregnancy Outcome Form
Question:

    `Was the baby born alive?' = Yes

AND
     'Gestation at pregnancy end:' = <37 weeks
   0
AND
      'Pre-PROM?' = Yes
   0
CRF: LOCI: 08. Maternal Outcome Form
Question:
   \circ 'Did the woman suffer preterm (<37 weeks) pre-labour rupture of membranes?' = Yes
   Gestational diabetes
CRF: LOCI: 07. Pregnancy Outcome Form
Question:
   \circ 'Was the baby born alive?' = Yes
AND
     'Gestational diabetes mellitus / type I diabetes / type II diabetes?' = Yes
   0
CRF: LOCI: 08. Maternal Outcome Form
Question:
   \circ 'Did the woman suffer gestational diabetes, diagnosed by GTT?' = Yes
Intrapartum outcomes:
   Chorioamnionitis
CRF: LOCI: 07. Pregnancy Outcome Form
Question:
   \circ 'Was the baby born alive?' = Yes
AND
       'Were there any intrapartum complications?' = Yes
   0
AND
   \circ 'Chorioamnionitis?' = Yes
```

```
Fetal growth restriction
•
CRF: LOCI: 07. Pregnancy Outcome Form
Question:

    Suspected IUGR = Yes

  Macrosomia
•
CRF: LOCI: 07. Pregnancy Outcome Form
Question:
     'Was the baby born alive?' = Yes
   0
AND
      'Fetal macrosomia?' = Yes
   0
Post-partum outcomes:
  Haemorrhage
•
CRF: LOCI: 08. Maternal Outcome Form
Question:
   • 'Did the woman suffer any other complications?'= Yes
AND
     'Haemorrhage?' = Yes
   0
Maternal outcomes:
   Admission to high dependency unit (HDU)
•
```

CRF: LOCI: 08. Maternal Outcome Form

Question:

 $_{\odot}$ `Was the participant admitted to HDU (level 2 care) prior to post-natal discharge?'= Yes

• Admission to intensive therapy unit (ITU)

CRF: LOCI: 08. Maternal Outcome Form **Question:**

 $_{\odot}$ `Was the participant admitted to ITU (level 3 care) prior to post-natal discharge?'= Yes

Neonatal outcomes:

Discharge to hospital

```
CRF: LOCI: 07. Pregnancy Outcome Form
Question:
• 'Was the baby born alive?' = Yes
```

AND

• 'Was the baby discharged from hospital? = Yes

AND

- 'Discharged to' = 'Other hospital'
 - Early infection

```
CRF: LOCI: 07. Pregnancy Outcome Form Question:
```

```
\circ 'Was the baby born alive?' = Yes
```

AND

• 'Early infection'= Yes

Retinopathy of prematurity

CRF: LOCI: 07. Pregnancy Outcome Form **Question:**

• 'Was the baby born alive?' = Yes

AND

• 'Retinopathy of prematurity requiring treatment?' = Yes

• Necrotising enterocolitis

CRF: LOCI: 07. Pregnancy Outcome Form **Question:**

 \circ 'Was the baby born alive?' = Yes

AND

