4.3. Primary outcome measure

The primary outcome is live birth at and beyond 34 completed weeks of gestation, as a proportion of all women randomised.

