5.3. Analysis populations

Participants will be analysed in the treatment group to which they were randomised, regardless of treatment compliance. Analysis populations will be as follows:

- Primary outcome, live birth at or beyond 34 weeks: all randomised participants. Analyses will also be produced using women who achieved pregnancy, defined as a positive pregnancy test (urine or serum beta-hCG test >10 mIU/ml), as the denominator but this will be treated as supportive evidence only)
- Secondary outcomes:
 - (Treatment outcomes) Ovulation rate, time from randomisation to pregnancy: all randomised participants
 - (Treatment outcomes) Number of ovulation induction cycles required for pregnancy: women who achieved pregnancy (defined as a positive pregnancy test (urine or serum beta-hCG test >10 mIU/ml))
 - (Pregnancy end outcomes) Ongoing pregnancy at 12 weeks (range 11⁺⁰ to 14⁺⁰ weeks) of gestation, pregnancy loss (defined as pregnancy loss <24 weeks of gestation), termination, stillbirth, molar pregnancy, pregnancy of unknown location, ectopic pregnancy, multiple live births: all randomised participants (analyses will also be produced using women who achieved pregnancy, defined as a positive urine or serum beta-hCG test >10 mIU/ml, as the denominator but this will be treated as supportive evidence only)
 - Time from conception to delivery (gestational age at live birth), gestational age <28/<32/<37 weeks, singleton live births at and beyond 34 completed weeks of gestation, live births at and beyond 37 completed weeks of gestation, mode of birth (unassisted vaginal, instrumental vaginal, elective caesarean section, emergency caesarean section, vaginal breech birth, other), number of ovulation induction cycles to live birth ≥24 weeks : women with live birth ≥24 weeks
 - Birth weight, APGAR score (at 1, 5 and 10 minutes) and APGAR score <7 out of 10 (at 1, 5 and 10 minutes): babies born alive ≥24 weeks
 - Antenatal outcomes: women achieving pregnancy
 - o Intrapartum outcomes: women with live birth≥24 weeks
 - Post-partum outcomes: women with live birth≥24 weeks
 - Maternal outcomes: all randomised participants

- Neonatal outcomes: babies born alive ≥24 weeks.
- Survival at 28 days of neonatal life: babies born alive ≥24 weeks
- Safety outcomes:
 - \circ Neonatal congenital or chromosomal abnormalities: babies born alive ≥24 weeks

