9.5. Analysis methods – primary outcome(s)

A template for reporting the primary outcome will be given in a separate template report.

The primary outcome is the proportion of women randomised who experience a live birth at and beyond 34 weeks of gestation. The denominator of this proportion will be all women randomised and the numerator will be those women who have conceived during the six ovulation induction cycles (maximum 240 days) and have gone on to have a live birth at or beyond 34 weeks.

A mixed effects binomial regression model will be used to calculate the risk difference (identity link) and relative risk (log link) with 95% confidence intervals for the primary outcome (live birth \geq 34 weeks), adjusting for the randomisation variables listed in section 4.6. If this primary method doesn't converge, the plan detailed in section 9.1 will be followed.

Statistical significance of the treatment group parameter will be determined (p-value generated) through examination of the associated chi-squared statistic (this will be obtained from the log-binomial model which produces risk ratios).

Summary data of the primary outcome in the form of frequencies and percentages will be produced that looks at the primary outcome for all the combinations of treatments (combinations A-D as per section 6.2 Baseline characteristics).

In the event of babies from a multiple pregnancy having different pregnancy outcomes, if at least one of the babies had a live birth \geq 34 weeks then this will count as a live birth \geq 34 weeks overall. If all those babies within that multiple pregnancy have the same pregnancy outcome (e.g. all are live births) then this will only be counted as one outcome (event).

See section 9.1 for covariate adjustment and model convergence.

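### SAP 9.4 derives the primary outcome by rules that conflict with its definition in SAP 4.3, 5.3 and 9.5: it excludes pregnancy losses, censors withdrawals and leaves out the 240-day conception condition

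*SAP*

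**What the plan says.** Three sections of the SAP define the primary outcome consistently. Section 4.3: "The primary outcome is live birth at and beyond 34 completed weeks of gestation, as a proportion of all women randomised". Section 5.3: "Primary outcome, live birth at or beyond 34 weeks: all randomised participants". Section 9.5: "The denominator of this proportion will be all women randomised", with the numerator limited to "those women who have conceived during the six ovulation induction cycles (maximum 240 days") who then have a live birth at or beyond 34 weeks. Section 9.5 adds that a multiple pregnancy counts as an event if at least one baby is live born at 34 weeks or later, and it fits a mixed effects binomial model.

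Section 9.4 tells the trial statistician how to build the variable. Its primary outcome entry repeats the all-randomised heading and uses two items from Form 07: baby born alive, and gestation at pregnancy end of at least 34 weeks. It then says "Exclude participants where: pregnancy outcome is miscarriage, ectopic, still birth or termination", and extends this to women with a live birth before 34 weeks. On women who withdraw or are lost before pregnancy end it says: "They will be censored at the point of withdrawal/lost to follow-up".

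The entry does not use the Form 04 item on pregnancy within 240 days of randomisation. The next derivation in the same section, cycles to live birth, does use it, as do time to pregnancy and cycles to pregnancy.

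**The concern.** Section 9.4 is the text a programmer would follow. Women with a miscarriage, ectopic pregnancy, stillbirth, termination or early live birth are treatment failures under the stated definition and belong in the denominator as non-events. Removing them conditions the primary result on something that happens after randomisation and may itself depend on treatment. A binary outcome in a binomial model has no censoring time, so the censoring instruction has no defined meaning there. Without the Form 04 condition, the programmed numerator is not the one in 9.5.

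This is the trial's only primary outcome and it feeds all five comparisons in SAP 4.12. Two statisticians, one working from 9.4 and one from 9.5, could produce different analysis datasets.

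**Working it through.** **Design figures first.** Power = Φ{[|p₁−p₂| − 1.96·√(2p̄(1−p̄)/n)] / √[(p₁(1−p₁)+p₂(1−p₂))/n]}, with n per arm, two-sided 0.05 and 1:1 allocation. Inputs are from SAP 4.7.

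- Comparison C, n = 380, 44% vs 34%: 80.8% (stated 81%).
- Comparisons A and B, n = 760, 39% vs 29%: 98.49% (stated 98.5%).

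Both reproduce. They rest on the definition in 4.3, 5.3 and 9.5, and the wording of 9.4 does not alter them.

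**The two rules side by side.**

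| Woman | SAP 4.3, 5.3, 9.5 | SAP 9.4 read literally |
|---|---|---|
| Miscarriage, ectopic, stillbirth, termination | 0 | removed |
| Live birth before 34 weeks | 0 | removed |
| Molar pregnancy, unknown location | 0 | not listed, so kept |
| Twins, one stillborn, one live born at ≥34 weeks | 1 | meets the exclusion |
| Conceived after 240 days, live birth at ≥34 weeks | 0 | 1 |
| Withdrawn or lost before pregnancy end | missing (9.3, 9.10) | censored, undefined |

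Molar pregnancy and pregnancy of unknown location count as pregnancy loss in 9.4's own pregnancy loss derivation, so similar failures would be handled differently.

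**Effect of literal exclusion.** If a share L of the women randomised is removed as failures, a true rate p becomes p/(1−L). With the same L in both arms, the relative risk is unchanged and the risk difference is multiplied by 1/(1−L).

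**Illustration from the protocol.** Section 1.2.2 gives one cited trial's counts: clomifene 62/209 conceptions and 47/209 live births; clomifene plus metformin 80/209 and 56/209. Assume every conception without a live birth is a loss.

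- Losses: 62 − 47 = 15 (15/209 = 7.2%) and 80 − 56 = 24 (24/209 = 11.5%).
- All randomised: 56/209 = 26.8% vs 47/209 = 22.5%; difference 4.3 points; RR 1.19.
- Losses removed: 56/(209−24) = 56/185 = 30.3% vs 47/(209−15) = 47/194 = 24.2%; difference 6.0 points; RR 1.25.

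**Applied to the design rates for A and B (39% vs 29%, true RR 1.345).** L is assumed.

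| L, higher-rate arm | L, lower-rate arm | Rates | Difference (points) | RR |
|---|---|---|---|---|
| 5% | 5% | 41.1% vs 30.5% | 10.5 | 1.345 |
| 11.5% | 11.5% | 44.1% vs 32.8% | 11.3 | 1.345 |
| 11.5% | 7.2% | 44.1% vs 31.3% | 12.8 | 1.41 |
| 7.2% | 11.5% | 42.0% vs 32.8% | 9.3 | 1.28 |

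With equal shares, 0.05 × 1520 = 76 to 0.115 × 1520 ≈ 175 women leave the denominator.

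**False-positive rate.** Suppose the true rate is 34% in both arms, with 760 per arm and L = 11.5% vs 7.2% (assumed). The rates become 0.34/0.885 = 38.4% and 0.34/0.928 = 36.6%, a spurious 1.8 points. The arms hold about 673 and 705 women, the pooled rate is 37.5% and its standard error about 2.61 points. So z ≈ 1.78/2.61 = 0.68, and the rejection probability is Φ(0.68−1.96) + Φ(−0.68−1.96) ≈ 10% instead of 5%.

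**The case against.** The best defence is that 'exclude' means 'do not count in the numerator'. The 9.4 entry is headed as a proportion of all women randomised, the sentence follows directly on the event criteria, populations are set in 5.3 and the model in 9.5, and 5.5 commits to strict intention to treat. Dropping miscarriages while keeping women who never conceived would contradict the entry's own heading. This is a fair reading. A reader might infer that the main analysis will use the wrong denominator; the documents do not show that.

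The defence does not cover everything. Under the numerator reading the 240-day condition is still absent and censoring is still undefined. A woman with one stillborn twin and one live born at 34 weeks or later is still ruled out by 9.4 and counted by 9.5.

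Other objections stand and limit the point:

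- **Missing outcomes.** A reader might see a further contradiction between 9.3, "In the first instance, analyses will be completed on received data only", and the all-randomised denominator. It is not an error. Complete-case analysis with a sensitivity analysis is declared in protocol 13.2.4 and SAP 9.3, and SAP 4.7 plans for outcome data on 760 of 800 and 1520 of 1600. 'Censored' is most naturally a misnomer for missing.
- **Late conceptions.** A reader might infer that births after later fertility treatment will be credited to the trial drugs. Section 9.5 states the window, and protocol 7.1 has end-of-study forms completed for women not pregnant by six months. The documents do not show how a later conception would reach Form 07.
- **Direction.** A reader might expect the arm with more conceptions always to gain. What matters is losses as a share of women randomised, and the bias can go either way.
- **Illustration.** The difference grows by about 40% (6.0/4.3), but the primary p-value comes from the relative-risk model, where 1.19 to 1.25 is about 5%. The contrast is exploratory comparison E. Conceptions minus live births is a proxy: it may include outcomes 9.4 does not list, and it cannot capture live births before 34 weeks.

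**Conclusion.** The point holds as an internal contradiction in the SAP. The 9.4 derivation, followed as written, does not produce the outcome defined in 4.3, 5.3 and 9.5. The window, the censoring and the multiple-pregnancy clash are defects under either reading of 'exclude'.

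The numerical harm from exclusion is conditional on the literal reading. Rates then rise wherever there are losses. The relative risk moves only if loss shares differ by arm; for shares of 7.2% and 11.5%, a design RR of 1.345 becomes 1.41 or 1.28 depending on which arm has more losses. Those shares are assumptions taken from a proxy in one cited trial. Sample size and power are unaffected.

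Because it concerns the primary outcome and the literal rule would give a wrong result, it should be corrected before the derivation is programmed and before the trial statistician is unblinded (SAP 5.6).

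**What to change.** Replace the primary outcome entry in SAP 9.4 with a three-way coding:

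- **1** if Form 04 shows pregnancy within 240 days of randomisation and Form 07 shows at least one baby born alive at 34+0 weeks or later.
- **0** for every other randomised woman whose outcome is known: no conception within the window, miscarriage, ectopic pregnancy, molar pregnancy, pregnancy of unknown location, termination, stillbirth, or live birth before 34 weeks.
- **Missing** if pregnancy status or pregnancy end is unknown, handled under 9.3 and the tipping-point analysis in 9.10.

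Delete the sentence excluding participants and the two sentences on censoring. Sections 4.3, 5.3 and 9.5 need no change to their definition of the outcome, and the complete-case approach can stay as declared.

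The cost is a few lines of SAP text and one derivation program. Both forms are already used elsewhere in 9.4, so no new data are needed.

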Appendix C: Schedule of assessments

			From randomisation							
Visit	Screening before clinic	Baseline clinic	Month 1	Month 2	Month 3	Month 4	Month 5	Month 6	Month 4-9*	Month 2-18**
Eligibility check	х	х								
Valid informed consent		х								
Relevant medical history taken	x	х								
Concomitant medication		х	х	x	х	х	х	х	х	х
Randomisation		х								
Routine blood tests	x	х								
D21 progesterone concentration blood test (where applicable)			x	x	x	x	x	x		
Dispensing of IMP		х								
Ultrasound monitoring of ovulation (optional, depending on local practice)			x							
Drug returns (participant visit)								x†		
Phone call to participant								х	x#	
EQ-5D-5L questionnaires		x							х	х
11-14 week ultrasound scan (if participant becomes pregnant)									х	
Final outcomes (conception failure; pregnancy, antenatal, intrapartum, post- partum, Day 28 neonatal and maternal outcomes)										х

*Exact month determined by when the participant becomes pregnant (e.g. if they become pregnant in month 1, subsequent assessments will be made in month 4). **Exact month determined by when participant becomes pregnant, and if they miscarry or have a successful live birth. †Pregnancy to be confirmed by month 6, visit 2 scheduled accordingly. #Second phone call to be made at week 15 of pregnancy.

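### SAP 9.4 scores cycles with no ovulation test, including cycles of conception, as non-ovulatory, so the ovulation rate is understated to the extent that cycles go untested

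*SAP*

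**What the plan says.** SAP 9.4 defines the outcome as "Ovulation rate (total number of ovulations / total number of ovulation induction cycles").

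- **Numerator.** It comes from form 03, completed per cycle: "Obtain total number of ovulations by totalling each 03. OI Drug Compliance and Ovulation Tracking Form per cycle where ovulation has occurred". Ovulation is recognised by any one of three positive records: an LH surge, progesterone above 20 nmol/l, or ultrasound tracking. The separate count of women who ovulated uses the same three criteria in any cycle.
- **Denominator.** It comes from form 04, from the item "Number of completed OI treatment cycles". Nothing requires that the cycle was assessed.
- **Testing.** Appendix C lists "D21 progesterone concentration blood test (where applicable") for months 1 to 6 and "Ultrasound monitoring of ovulation (optional, depending on local practice") for month 1 only.
- **Missing data.** Section 9.3 says "In the first instance, analyses will be completed on received data only" and has no rule for a single unassessed cycle. Section 9.10 limits sensitivity analyses to the primary outcome.
- **Analysis.** Section 9.6 fits a fractional logit model and reports a mean difference in proportions. Section 5.3 takes all randomised women as the population.

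On the lesser point, 9.4 derives gestational diabetes from a form 07 item, "Gestational diabetes mellitus / type I diabetes / type II diabetes?' = Yes", joined to a live-birth condition, and then lists a form 08 item for diabetes diagnosed by glucose tolerance test. Pregnancy-induced hypertension and pre-eclampsia share one form 07 item, "Hypertension / pre-eclampsia?' = Yes", also joined to a live birth, and each has its own form 08 question. No AND or OR is written between the forms.

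**The concern.** The numerator needs a positive test and the denominator does not need a test at all. A cycle in which nobody looked is then indistinguishable from a cycle in which ovulation was sought and not found. The clearest case is conception: it proves ovulation, yet without one of the three records that cycle adds nothing to the numerator.

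Ovulation rate is the first treatment outcome listed in SAP 4.4, and inducing ovulation is what letrozole and clomifene are given for. Attenuation would make the two drugs look more alike on this outcome than they are. If coverage differed between arms, the rule could also produce a difference where none exists.

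**Working it through.** The plan gives no ovulation rate and no testing coverage, so there is no figure of its own to reproduce. The check applies the written rule literally, then shows its size over a range of assumed coverage.

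**Step 1. Is a conception cycle in the denominator?** The same form 04 item supplies the number of cycles needed for pregnancy and for live birth. Section 9.6 reports cycles to live birth as values from 1 to 6, so a conception in cycle 1 must be recorded as 1. The conception cycle is counted.

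**Step 2. One woman.** She conceives in cycle 1 with no LH, progesterone or ultrasound result.
- Rule as written: 0/1 = 0%, and she is absent from the count of women who ovulated.
- Conception accepted as evidence: 1/1 = 100%.

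**Step 3. Whole arms.** If a share t of cycles is tested, independently of ovulation, the expected reported rate is t × true rate, and the difference is t × true difference.

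Assumed inputs, none from the documents: ovulation in 80% v 70% of cycles; conception in 15% of ovulations; up to 6 cycles, stopping at conception; 400,000 simulated women per arm. The true woman-level means are about 83% and 74%, a difference of 9.0 points. By the formula, 0.8 × 9.0 = 7.2 and 0.6 × 9.0 = 5.4.

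| Coverage | SAP rule, means | SAP rule, difference | Proposed rule, means | Proposed rule, difference |
|---|---|---|---|---|
| 100% | 83.0% v 73.9% | 9.0 | 83.0% v 73.9% | 9.0 |
| 80% | 66.4% v 59.1% | 7.3 | 83.6% v 74.8% | 8.8 |
| 80%, but 50% in conception cycles | 58.8% v 52.5% | 6.4 | 83.6% v 74.8% | 8.8 |
| 60% | 49.8% v 44.3% | 5.4 | 84.5% v 76.0% | 8.5 |

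Differences are in points and were taken before rounding. The proposed rule counts conception cycles as ovulatory and drops other untested cycles; women with no usable cycle are left out.

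**Step 4. Unequal testing.** With ovulation at 80% per cycle in both arms but coverage of 80% v 70%, the SAP rule alone gives a difference of 8.4 points. The proposed rule gives 0.4 points or less in size.

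**Step 5. Bias of the remedy.** Conception cycles always enter, while untested other cycles drop out. Per cycle, at 60% testing:
- true 70%: (0.105 + 0.595 × 0.6) / (0.105 + 0.895 × 0.6) = 0.462/0.642 = 72.0%
- true 80%: (0.12 + 0.68 × 0.6) / (0.12 + 0.88 × 0.6) = 0.528/0.648 = 81.5%

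That is an upward bias of 2.0 and 1.5 points.

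**Step 6. Forms 07 and 08.** The two possible connectors give different errors.

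| Reading | Gestational diabetes | Hypertensive outcomes |
|---|---|---|
| OR | Type I or II diabetes alone is counted | Either disorder counts in both outcomes |
| AND | Cases without a live birth are lost | Cases without a live birth are lost |

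The AND loss conflicts with section 5.3, where the antenatal population is women achieving pregnancy. To size the OR reading, assume 10% gestational diabetes, 1% to 5% pre-existing diabetes and a true relative risk of 1.5. The reported rate becomes 11% to 15%. The relative risk becomes (0.15 + 0.01)/(0.10 + 0.01) = 1.45 down to (0.15 + 0.05)/(0.10 + 0.05) = 1.33.

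**The case against.** **Testing may be nearly complete.** Progesterone is scheduled in every month from 1 to 6, an LH surge is a third route, and SAP 4.2 lets the dose rise until ovulation is confirmed, so some assessment is expected in care. This stands as a limit on size. A reader might infer that the reported ovulation rate is certain to be wrong; the documents do not support that, because they give no coverage and complete testing removes the error. The dosing argument also cuts the other way: testing could lapse once ovulation is established, though the documents do not say so.

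**The SAP never says that an untested cycle is non-ovulatory.** True, but the stated ratio has that effect, and section 9.3 supplies no rule that would prevent it.

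**Blinding should keep testing balanced between arms.** This makes a spurious difference less likely than simple attenuation. Step 4 is a what-if, not a prediction.

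**The ratio might be thought to exceed 1** because its two parts come from different forms. That would need a data discrepancy between forms, which data queries exist to catch. It is a minor reason to use one form.

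**Diabetes and hypertension.** A reader might infer that 9.4 counts type I and II diabetes as gestational diabetes, or that the two hypertensive outcomes cannot be separated. Neither is established. Both need an OR that is not written, and form 08 asks about each condition separately. Other two-form rules in 9.4 that lack a connector, such as singleton live birth and cycles to live birth, only make sense as AND. Against that, the insulin-resistance subgroup in the same section does write OR between the form 07 and form 08 diabetes routes, with extra conditions on the form 07 side. The OR and AND errors cannot both occur. What stands is that the rule is ambiguous and each reading has a fault.

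**Conclusion.** The ovulation point holds on the written rule. Untested cycles, including conception cycles, are scored as non-ovulatory, and no other section corrects this. The understatement is roughly proportional to the untested share: under the assumed rates, 9.0 points becomes 7.3 at 80% testing and 5.4 at 60%. Those sizes rest on assumed ovulation, conception and coverage figures, and on testing being unrelated to ovulation except where stated. The direction does not rest on them, provided coverage is similar in the two arms.

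The form 07 and 08 point is held with less confidence and goes no further than a missing connector around a compound item.

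A reader might also take ovulation rate and gestational diabetes to be designated mechanism outcomes, or gestational diabetes to be a main metformin question. The SAP lists them as a treatment outcome and an antenatal outcome, and its stated metformin question is live birth. All are secondary outcomes reported with confidence intervals, and the primary analysis is untouched. The change should be made, but the trial's main conclusion does not depend on it.

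**What to change.** In SAP 9.4:

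1. Score the conception cycle as ovulatory, both in the ovulation rate and in the count of women who ovulated.
2. Treat a cycle with no ovulation assessment and no conception as missing.
3. Take numerator and denominator from the same per-cycle form 03 records.
4. Report the share of cycles assessed, by arm.
5. Keep the all-cycles denominator as a sensitivity analysis, and extend 9.10 to allow it.
6. Base gestational diabetes, pregnancy-induced hypertension and pre-eclampsia on their specific form 08 items, without the live-birth condition. Section 9.4 already uses form 08 alone for obstetric cholestasis. Where two forms are kept for any outcome, write AND or OR.

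The cost is derivation wording, with no new data collection. Items 1 and 2 leave fewer cycles where sites did not test, and add a small upward bias (about 1.5 to 2 points at an assumed 60% testing and 15% conception per ovulation). Item 4 lets readers judge that bias. Item 6 gives up cases reported only on form 07, so the completeness of form 08 should be checked first.
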